APPENDIX

1. Subject Participation Flow

Prospective/Potential Participant is informed about joining the COVID-19 Readiness Cohort and to visit United in Research to create a Citizen Scientist profile (or if they are already registered – they can log into their existing profile and review and choose to join the COVID-19 Readiness Cohort

For those who are willing/interested, a Citizen Scientist profile is created (the profile collects the following information: name, age, best contact information including cell phone number, and whether the person has UHC insurance)

After creating a profile, the Citizen Scientist is now eligible to pre-enroll into the COVID-19 Readiness Cohort to be placed on the waiting list for notification that their area was selected due to location to product supplier for the Lilly product and Optum Infusion Nurses

During pre-enrollment, additional information is collected from the Citizen Scientist – specific to information needed to determine eligibility for the Lilly product study (this includes: confirming home address, height/weight, race/ethnicity, any potential exclusions such as pregnancy, cancer, transplants, transfusions, or COVID vaccines, confirmation that they are willing to use a smartphone app for symptom tracking (Protect Well), willingness to do COVID testing – either at home and mail it back, at a clinic or that either is fine and willingness to consent to the Lilly product trial)

After reviewing what they are agreeing to (the COVID-19 Readiness Cohort Consent) – if they choose to join, they are on the waiting list for location selection eligibility determination (along with individual eligibility determination from that point forward – but the first step is picking a location where they can reasonably receive the product and have it infused)

If their area is selected as a Lilly product eligible site – the pre-enrolled Citizen Scientists in the COVID-19 Readiness Cohort in that area will receive an automated email notification (to whatever preference email they have in United in Research or a text message if that was their preferred method of contact) that they are now eligible to enroll into symptom tracking via Protect Well and will provide instructions for how they should do that and begin tracking

If symptomology in the ProtectWell app indicates likely COVID-19 infection, a kit would be expedited (if they are not in Well At Home) to the house address for the participant to complete/return

If symptomology in the ProtectWell app indicates likely COVID-19 infection, the registered participant would receive notification of how to proceed with completing the test kit and sending in/processing for results

In either scenario, once the kits are completed/returned and COVID-19 infection is confirmed via the test, the participant becomes eligible to move forward into actively participating in the Lilly product trial and UHG R&D will flag them as ready to schedule the at-home infusion

At-home infusion appointment is scheduled – aligning with product preparation and considerations for site specific travel times and product shelf-life after preparation – and confirmed with those in the household receiving the infusion

At-home infusion occurs, and proper protocol is followed for infusion of the product and monitoring those who received it for any unexpected effects after receipt of the product

After at-home infusion, the household will be tracked via the ProtectWell app and any specific symptom/side effect tracking mechanisms in the United in Research platform will also occur to monitor how the participants are doing

If any issues develop during the active follow-up period, the issues will be presented to Lilly (if they are medical/clinical in nature – not logistical or operational issues) for consideration of: 1) how to address for the particular participant (or whether any action is required) and 2) if the issues reported warrant informing the FDA

[figure not shown]

At completion of the active follow-up period data will be compiled and prepared and shared with Lily for review/analysis in order to produce interim findings (and any unexpected findings) during active conduct of the study

Once a participant has completed their active follow-up phase, we will either thank them for their participation and consider them as completed (informing them that we will circle back with results of the project) or if there is any advantage to keeping them tracking for long-term response or effects, we could develop a long-term follow-up mechanism (i.e. please do inform us via United in Research if you start developing symptoms again or if a member of the household gets sick)

2. Subject Participation Flow Visual

3. Wellness check plan and clinical connection

Instructing Patients for Using ProtectWell Wellness Check via the App Post-Infusion from Day 1 – Day 28

Rating system:

- Using a 1 – 10 system (1 = the worst you can feel and 10 = feeling great)
- Grouping:

- 1-3 rating (potential flag for clinical outreach)
 - 4-7 rating (feeling OK – no action needed)
 - 8-10 (feeling good/great – no action needed)
- Day 1 rating dictates baseline for Days 2-28
 - Goal is for patients to either stay steady at Day 1 rating or to continue to see an increase as they progressively feel better
- Rating drops between Day 2 and Day 28
 - If rating drops back to a 4 or above from where the patient was (for example – registered a 6 and the next day registered a 4) – no clinical follow-up at that time but will get a note recognizing that they took a step back in their ratings
 - If rating drops back to 3 or below from where the patient was (for example – registered a 5 and the next day registered a 3) – this would trigger clinical outreach by the UHG Clinical Team
- Post-Infusion Day 1 – Baseline
 - It is fine to start at a 1-3 (and likely expected as these folks have COVID-19 and even though symptoms are mild to moderate – they are probably not feeling too well)
 - It is fine to stay in the 1-3 range for a few days if they are either:
 - Staying the same as baseline
 - Seeing minor increases (for example – going from a 1 to a 2 or a 2 to a 3)
 - If the patient continues to check the same rating but does not get above a 3 – this would be flagged for clinical follow-up – the clinical lead will assess what day of the experience the participant is in and either flag them for clinical follow-up connection or document permitting another wellness day check-in to see if the level of wellness improves
- Clinical Follow-up/Outreach During 28-day active period
 - UHG R&D internal clinical team (leadership role is a RN) will review the twice daily reports that have extracted any participants who have a 1-3 rating
 - This report will dictate who requires clinical follow-up/outreach or it will be documented as to the reason why clinical connection was not (see example above – closer to day 1 post-infusion)
 - Clinical follow-up will occur with consistency by using the “Symptoms List for Clinical Outreach and Action Plan”
 - Information collected during clinical follow-up will be consistently documented in the participant file and reports for symptoms and other issues being reported will be generated for assessment as needed (i.e. aggregate reports for assessing severity/frequency of events as needed)
 - Clinical action taken in response to reported symptoms/issues will also be documented
- Overall goal
 - Patients will progress from the lower numbers to the higher range numbers during the 28-day period (with hopefully a good jump from initial receipt of infusion)

4. Symptom checker and clinical action

Participant ID:

Assessment Date: (DD/MMM/YYYY)

High priority**Cough – requires immediate medical attention if *severe* symptoms reported**

- Yes
 - Mild
 - Moderate
 - Severe
- No (Absent)

High priority**Shortness of breath – requires immediate medical attention if *moderate to severe* symptoms reported**

- Yes
 - Mild
 - Moderate
 - Severe
- No (Absent)

High priority**Feeling feverish – requires immediate medical attention if *high* fever is reported. For *moderate* fever, clinical call required**

- Yes
 - Low grade (<100 degrees F)
 - Moderate – (100-102 degrees F)
 - High (anything above 102 degrees F)
- No (Absent)

High priority**Chills/Shaking – requires immediate medical attention if *severe* symptoms reported (severe symptoms being “shaking chills” – i.e. teeth chattering, body shakes)**

- Yes
 - Mild
 - Moderate
 - Severe
- No (Absent)

Body aches and pain – requires immediate medical attention if *severe* symptoms reported

- Yes
 - Mild
 - Moderate
 - Severe
- No (Absent)

Fatigue**Headache**

- Yes
 - Mild
 - Moderate
 - Severe
- No (Absent)

Loss of taste

Yes
 Mild
 Moderate
 Severe
 No (Absent)

Sore throat

Yes
 Mild
 Moderate
 Severe
 No (Absent)

Loss of appetite

Yes
 Mild
 Moderate
 Severe
 No (Absent)

Yes
 No

Loss of smell

Yes
 No

Nausea

Yes
 Mild
 Moderate
 Severe – how often _____
 No (Absent)

Nausea

Yes
 Mild
 Moderate
 Severe – how often _____
 No (Absent)

Diarrhea

Yes
 Mild
 Moderate

Severe – how often _____

No (Absent)

Are you experiencing any additional symptoms/health issues beyond what was just asked above?

Yes

No

If yes – please explain:

Overall, how bad are your symptoms TODAY?

No symptoms

Mild

Moderate

Severe

Very severe

Overall, how is your general physical health TODAY?

Poor

Fair

Good

Very good

Excellent

For any issues reported or discovered that may meet the following criteria, please contact [name] immediately at [contact] or [contact] to report:

Event is **likely related to bamlanivimab** and is **both unexpected and serious** (see outcomes below for serious adverse events) →

Event outcomes resulted in:

- 1) Death
- 2) Life-threatening adverse drug experience (meaning determined related to bamlanivimab)
- 3) Inpatient hospitalization or prolongation of existing hospitalization (for > 24 hours) *already being checked for due to primary efficacy endpoint
- 4) Persistent or significant incapacity or substantial disruption of the ability to conduct normal life functions
- 5) Congenital anomaly/birth defect
- 6) Important Medical Event (IME) that may not result in death, be life threatening, or require hospitalization may be considered a serious adverse drug experience when, based upon medical judgment, it may jeopardize the patient or subject and may require medical or surgical intervention to prevent one of the outcomes listed in this definition

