5.3 Eligibility

Both study participants and matched controls will meet the inclusion and exclusion criteria below.

Inclusion Criteria:

- Age 65+, confirmed SARS-CoV-2 positive, located in an area where Bamlanivimab (LY3819253) is available for infusion,
- Have mild or moderate COVID-19 symptoms (after stage 1 of symptom tracking)
- Control only: seek care at an OptumCare facility for confirmed symptomatic COVID-19

Exclusion Criteria:

- Current (from first symptom report) hospitalization for COVID-19
- Prior administration of Bamlanivimab

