6.2 Subject Participation

Enrolled in COVID-19 Readiness Cohort

- If located in an area where at-home infusion of Bamlanivimab is available, screened for detailed eligibility and begin symptom tracking upon determining eligible
- If symptoms begin to develop, receive COVID-19 test at home
- If COVID-19 positive, home infusion visit is scheduled/confirmed for enrolled participant

Please see Appendix 1 & 2 for additional detail.

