4.4.2 Patient Groups

Before analysis there are two study populations – study participants and the pool of potential controls. For study participants, we plan to enroll aged 65 and older, who are deemed high risk per the emergency use authorization, if contracting COVID-19. For the pool of potential controls, we plan to utilize UHC members who have Optum EMR data to confirm presence of symptoms during COVID test as well as having continuous enrollment to access to their claims and prospective hospitalization and death data. If applicable, non-UHC members or UHC members who did not seek care at OptumCare facilities may be used as members of the control population based on EMR review and matching to enrolled participants.

During analysis (i.e., after matching), there will be two study populations – study participants after matching and matched controls. Note that the size of study participants after matching may be smaller than the size of original study participants if a matched control can't be identified.

The targeted number of enrolled participants for tracking for symptoms is 500,000, and the targeted number of study participants who are COVID-19 positive and consent to receive Bamlanivimab (LY3819253) is 7,500. Figure 2 illustrates the process to identify study participants. Regarding controls, we set the case:control ratio at 1:1 and plan to identify 7,500 matched controls which is the same as number targeted for study participants.

Given the current enrollment speed (as of March 9, 2021) and the decreasing COVID-19 hospitalization rate across the US, we may not achieve the target number of study participants, 7,500. However, according to the power analysis in Section 4.3, it is sufficient to have 1,000 study participants with another 1,000 matched controls to detect a 33% decrease in the hospitalization rate (i.e., from 15% to 10%) with power 0.8 and level 0.05.

Commented [JAT7]: Remove as treatment is allowed in this situation per the EUA.

Commented [JAT8]: Remove prior vaccination from exclusion criteria as this is not required per the EUA.

Commented [WWY9]: Should we replace continuous member enrollment?

Commented [WWY10]: Given current enrollment speed, it will be helpful to show what is the minimal sample size for Bam treated group required for the primary objective analysis.

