Table A8. Standardized difference in mean and variance ratio of the propensity score and all matching covariates before propensity score matching

Commented [XM58]: Would report both results before and after match

Variable	Standardized difference in mean	Variance ratio
Propensity score		
Age (continuous or categorical):		
65-		
65 – 69		
70 – 74		
75 – 79		
80+*		
*: We can separate 80+ into finer groups as needed.		
Gender		
Race:		
White		
Black		

LY3819253

CONFIDENTIAL

[Protocol number: UHG (J2X-NS-I002)] SAP [\[v.3\]](#)

Asian	
Hispanic	
Other	
Urbanization of residence:	
Urban	
Suburban	
Rural	
Socioeconomic index	
Dual status	
With Medicaid	
Elixhauser comorbidity score	
Elixhauser conditions [*]	
[*] : There are 29 conditions in total as shown in Table A1.	
Immunosuppressive treatment 6 months prior to date of COVID diagnosis	

Dataset: dataset location (data table name with the corresponding database in Google BigQuery)

Program: program location/program name.R

Output: output location/output name.csv or .xlsx

Repeat Table A8:

Table A8.2

Standardized difference in means and variance ratio of the propensity score and all matching covariates after propensity score matching

Propensity score matched population

Programming notes:

Replace “before propensity score matching” with “after propensity score matching” in the table title.

LY3819253

CONFIDENTIAL

[Protocol number: UHG (J2X-NS-I002) SAP [v.3]

Table A9. Unadjusted and adjusted measures of COVID-19 hospitalization risk in study participants and matched controls.

Outcome	Results (e.g., 95% CI and p-value)
Rate of COVID-19 hospitalization w/o considering censoring on Day 28 (i.e. binary endpoint) among study participants vs matched controls	
Adjusted odds ratio w/o considering censoring on Day 28 (i.e. binary endpoint) among study participants vs matched controls	
Adjusted hazard ratio with considering censoring on Day 28 among study participants vs matched controls	

Commented [XM59]: Would include 95% CI and p value.

Commented [XM60]: Not sure what this mean?

Commented [JAT61R60]: This means a binary response. If we don't observe a covid-19 hospitalization for a patient within 28 days after his/her treatment, we define this response as 0, instead of censoring on Day 28.

Dataset: dataset location (data table name with the corresponding database in Google BigQuery)

Program: program location/program name.R

Output: output location/output name.csv or .xlsx

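### COVID vaccination is no longer an exclusion but is in no covariate list or balance table, and the potential exclusions in Protocol Appendix 1 do not match Protocol 5.3

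*Protocol*

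**What the plan says.** Protocol 5.3 opens by stating that "Both study participants and matched controls will meet the inclusion and exclusion criteria below". It then gives two exclusions: "Current (from first symptom report) hospitalization for COVID-19" and "Prior administration of Bamlanivimab". SAP 4.4.1 gives the same two.

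Protocol Appendix 1, the participation flow, describes a pre-enrollment step that collects information "specific to information needed to determine eligibility for the Lilly product study", including "any potential exclusions such as pregnancy, cancer, transplants, transfusions, or COVID vaccines". Protocol 6.2 adds that participants are "screened for detailed eligibility and begin symptom tracking upon determining eligible". Controls are not enrolled. SAP 4.2 and 5.8.1.2 draw them from EMR and claims data, so they never answer these questions.

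On vaccination, a margin comment in the SAP's study-population section reads: "Remove prior vaccination from exclusion criteria as this is not required per the EUA". The current criteria agree with that comment. Vaccination is then absent from:
- the variable lists in Protocol 4.4 and SAP 4.7;
- the outcome-model covariates named in SAP 5.2;
- the matching variables in SAP 5.8.1.2;
- the mock tables, including Table A8, which is meant to show "all matching covariates before propensity score matching";
- the unmeasured confounders named in SAP 5.8.2.

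**The concern.** The two protocol texts cannot both be the eligibility rule. One is a two-item list for both groups. The other is a longer list of possible exclusions put to participants only. A reader cannot tell which list formed the treated group.

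The statistical issue is what follows from dropping vaccination as an exclusion. A restriction on a prognostic factor controls for that factor. Once the restriction goes, the factor has to be handled by matching or adjustment, and nothing in the plan does this. The comparison is not randomized, and SAP 5.8.2 itself says its validity depends on the right confounders being measured and included. Vaccination plausibly affects admission risk. It may also be distributed differently between volunteers in a symptom-tracking study and patients found in medical records. An imbalance could create an apparent benefit or hide a real one.

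**Working it through.** **Texts side by side.** Of the five items in Appendix 1, none appears in Protocol 5.3 or SAP 4.4.1. What the matching plan covers for each:
- Cancer: lymphoma, metastatic cancer and solid tumor are three of the 29 Elixhauser conditions (SAP Table A2). They are candidate covariates and fall under the Elixhauser row of Table A8, from 2019 data only.
- Transplant: not an Elixhauser condition. It is partly proxied by the immunosuppressive prescriptions in SAP Table A3.
- Pregnancy: immaterial at age 65 and over.
- Transfusion: no named covariate.
- COVID vaccination: no named covariate and no direct proxy. Test date is a listed variable, and a reply in the SAP 4.7 margin says it will help find controls infected at about the same time. Test date is not a row in Table A8, and two people infected on the same date can still differ in vaccination.

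**The plan's own figure.** SAP 4.4.2 says 1,000 per group suffice to detect 15% versus 10% with power 0.8 at level 0.05. Using n = [1.96·√(2·0.125·0.875) + 0.8416·√(0.15·0.85 + 0.10·0.90)]² / 0.05² gives 686 per group (726 with continuity correction), and 1,000 per group gives power 0.92. The statement holds, and no sample-size figure is disputed here.

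**Illustration of bias.** Every vaccination input is an assumption. If vaccination halves admission risk, a group with vaccinated share v has relative rate 1 − 0.5v.
- 30% of participants and 10% of controls vaccinated, no drug effect: (1 − 0.15)/(1 − 0.05) = 0.85/0.95 = 0.89.
- Shares reversed: 0.95/0.85 = 1.12.
- With the plan's target effect of 10/15 = 0.67 and the same imbalances: 0.667 × 0.895 = 0.60, or 0.667 × 1.118 = 0.75. The apparent reduction is then 40% or 25% instead of 33%.

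**Range at 1,000 per group** (normal approximation, pairing ignored). Let v be the vaccinated share in one group, with none in the other, and r the vaccinated-to-unvaccinated risk ratio. Take v from 5% to 30% and r from 0.2 to 0.6.
- Vaccinated people among participants only, no drug effect, 15% baseline: the spurious reduction is v(1 − r), from 0.05 × 0.4 = 2% to 0.30 × 0.8 = 24%. The two-sided rejection rate runs from 5% to 66% instead of 5%.
- Vaccinated people among controls only, true rates otherwise 15% and 10%: the control rate is 0.15·[1 − v(1 − r)], from 14.7% down to 11.4%. The apparent reduction falls from 33% to between 32% and 12%, and power from 0.92 to between 0.89 and 0.17. For example, v = 20% and r = 0.4 give 0.15 × 0.88 = 13.2%, a reduction of 1 − 0.10/0.132 = 24%, and power 0.61.

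**The case against.** A reader might infer that people with cancer, a transplant or a vaccination are barred from the treated group but not from the controls. The documents do not show this. Appendix 1 speaks of potential exclusions, describes information gathered before a waiting list, and never says that a positive answer prevents enrollment. The formal criteria in the two documents agree, and the SAP comment shows vaccination was taken out deliberately. Leftover wording is the likelier explanation.

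A reader might also infer that the groups would differ on cancer and transplant. If cancer patients were filtered out of the treated group, a propensity model that kept the cancer flags would give such controls low scores, and few would be matched. Transplant is partly covered by the drug list. The limits are that the comorbidity flags come from 2019 and must survive covariate selection.

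Nor is it right that nothing planned bears on vaccination. The intended use of test date, with age, region and nursing-facility residence, captures part of what drives uptake. The covariate set is also open: SAP 5.8.1.1 admits further clinical attributes where available, and SAP 5.2 has the final list confirmed before outcome analysis. Vaccination could therefore enter under existing text, but nothing commits the analysis to it. The E-value and the proportion of unmeasured confounding are optional in SAP 5.8.2; they gauge robustness and correct nothing.

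Finally, the magnitudes are assumptions, and at the low end the effect is negligible. That is fair, and they are offered only as a scale.

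**Conclusion.** Two things stand. First, Appendix 1 and Protocol 5.3 are inconsistent in current text and must be reconciled. That is probably an editorial matter, and no view is taken here on which exclusions are clinically right. Second, vaccinated people may be in either group, and the plan as written neither balances nor adjusts for vaccination, nor names it as a residual confounder. Calendar-time matching reduces this gap but does not close it.

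The size is unknown from the documents. If vaccination halves risk and the shares are 30% and 10%, the spurious risk ratio is about 0.89, against a target of about 0.67. The bias can run in either direction, and it is nil if the shares are equal after matching. The point should be settled before outcome data are accessed, but it does not undermine the sample-size calculation or the cancer covariates.

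**What to change.** - Reconcile Protocol Appendix 1 with Protocol 5.3 and SAP 4.4.1, and apply the one resulting list to both groups.
- Add vaccination status before the positive test to SAP 4.7, to the propensity and outcome models, and to Table A8.
- Take it from the same type of source in both groups, claims or EMR, as of the test date. SAP 5.1.1 says the analysis populations are UHC members, for whom SAP Table 1 lists claims in both groups. Pre-enrollment answers should not be the main source: symptom tracking can last up to 6 months, so they may be out of date at the positive test. Setting self-report in one group against records in the other would also build in differential measurement. Participants' self-report, updated at symptom report or infusion, can serve as a supplement or check.
- Add a sensitivity analysis limited to people with no vaccination record.
- Name residual vaccination misclassification in SAP 5.8.2.

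The cost is protocol and SAP wording and one more data pull. The main drawback is incomplete vaccination records. A person with no record may still have been vaccinated, so the restricted analysis reduces the problem without removing it.

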2. STUDY PURPOSE & OBJECTIVES

The purpose of this study is to: Assess the safety of at-home infusion of Bamlanivimab and to determine whether symptomatic high risk COVID-19 participants will have a reduction in hospitalizations compared to a real-world external control population when provided with a combination of symptom tracking and single dose administration of Bamlanivimab (LY3819253) via an at-home infusion visit.

The primary objectives are:

Safety

- To describe the incidence of infusion reactions during receipt of infusion and during the defined infusion follow-up period
- To describe the incidence of patient reported adverse event outcomes through Day 28

Efficacy

- To determine the incidence of COVID-related hospitalization at Day 28 among Bamlanivimab-treated participants (**long-term** – hospitalization rate via medical records/claims data and **short-term** via participant self-report during active study participation) relative to external controls.

The exploratory objective is:

- To determine the incidence of COVID-related mortality at Day 28 among Bamlanivimab-treated patients relative to external controls.

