6.5.5 Secondary safety outcome analysis: Adverse events

Research Questions:	Data Variables:	Data Source:

Do we find any self-reported adverse events between receipt of infusion and day 28 from study participants?
 
Do patient-reported adverse events vary from demographic characteristics or comorbidities?
	
 • Date of infusion treatment • Date of infusion reactions of interest • Demographics • Elixhauser conditions 	
 • Patient self-reported data • Optum infusion nurse data • UHC claims data

Once adverse events are defined or classified and adjudicated, we can perform the same methodology described in 6.5.4.

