5.10 Safety Analyses

The two safety objectives are:

1. To describe the incidence of infusion reactions during receipt of infusion and during the defined infusion follow-up period (follow-up period to be consistent with EUA fact sheet for healthcare providers)
2. To describe the incidence of patient reported adverse event (AE) outcomes through Day 28

Commented [WWY50]: This section should add such as Reporting by System Organ Class (SOC) and PT. Please refer to the sample SAP

Commented [JA51R50]: We're checking internally and will keep you posted.

Objective:	Data Variables:	Data Source:
Identify any infusion reactions during receipt of infusion and during the infusion follow-up period	
 Infusion reactions Date of infusion treatment Date of infusion reactions of interest Demographics Elixhauser conditions 	
 Optum infusion pharmacy data UHC claims data

Clinicians will start with qualitative analysis a case by case. We will report descriptive statistics according to the data we will obtain. If we have a sufficient size of study participants with particular infusion reactions, we can calculate descriptive statistics, run Chi-square independence test and Kruskal-Wallis test to examine if infusion reactions vary from demographics or comorbidities.

Objective:	Data Variables:	Data Source:
Identify any self-reported adverse events between receipt of infusion and day 28 from study participants	
 • Adverse events • Date of infusion treatment • Date of infusion reactions of interest • Demographics • Elixhauser conditions 	
 • Optum infusion pharmacy data • UHC claims data

We will perform the same methodology described above given the AEs and serious AEs defined in Section 5.10.1.2.

5.10.1.1 **Extent of Exposure**

Exposure to therapy will be represented as the total number of complete and incomplete infusions, and will be summarized using descriptive statistics.

Commented [ATJ52]: To Lilly: I'm not sure what requires in this section and if we need it.

Commented [XM53]: Exposure to therapy will be represented as the total number of complete and incomplete infusions, and will be summarized using descriptive statistics.

Commented [JAT54R53]: Thanks. Added the texts.

5.10.1.2 **Adverse Events**

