The current list of AEs comes from the Phase 2 trial of ambulatory participants and a reasonable anticipation of serious AEs for this study.

The most commonly reported AEs from the Phase 2 trial include:

- Nausea
- Diarrhea
- Dizziness
- Headache
- Pruritus
- Vomiting

The reasonably anticipated serious AEs include:

- Secondary infection – pneumonia, sepsis
- Respiratory failure requiring non-invasive or invasive mechanical ventilation – acute respiratory distress syndrome (ARDS)
- Major acute cerebrocardiovascular event – cardiovascular death, myocardial infarction, hospitalization for unstable angina, hospitalization for heart failure, serious arrhythmia, resuscitated sudden death, cardiogenic shock due to myocardial infarction, coronary revascularization procedure, neurologic stroke, and peripheral vascular events
- Coagulopathy
- Acute kidney injury – renal replacement therapy
- Multi-organ dysfunction syndrome

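### The Day 28 patient-reported adverse-event incidence will be under-ascertained: no event question is scheduled for all infused participants, and the SAP does not name the follow-up records as a source

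*Protocol*

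**What the plan says.** Protocol section 2 places this among the primary objectives: "To describe the incidence of patient reported adverse event outcomes through Day 28". Protocol 6.5 and SAP 3.3 call the same objective secondary.

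After the infusion visit, Protocol 6.1 and 6.4 schedule one daily wellness score from 1 to 10. Appendix 3 attaches actions to the score bands: "4-7 rating (feeling OK – no action needed" and "8-10 (feeling good/great – no action needed". Clinical outreach follows "If rating drops back to 3 or below from where the patient was", or a score that stays at 3 or below. In that second case the clinical lead may instead "document permitting another wellness day check-in to see if the level of wellness improves". The symptom list (Protocol Appendix 4) is the tool for that outreach, and the UHG R&D clinical team documents the findings in the participant file.

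Protocol 9.1 describes the trigger differently: a participant who marks feeling worse gets a phone follow-up, and one who feels the same or better needs none.

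For the analysis, Protocol 6.5.5 asks "Do we find any self-reported adverse events between receipt of infusion and day 28 from study participants" and lists three sources: patient self-reported data, infusion nurse data and claims. SAP 5.10 keeps the aim, "Identify any self-reported adverse events between receipt of infusion and day 28 from study participants", but lists only Optum infusion pharmacy data and UHC claims. SAP 4.7 (Phase II.B) gives pharmacy data alone for the adverse-effect variables. SAP 5.14 records no change from the protocol. SAP 5.10.1.2 introduces its six events with "The most commonly reported AEs from the Phase 2 trial include": nausea, diarrhea, dizziness, headache, pruritus and vomiting. The Table A12 footnote repeats these six.

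**The concern.** An incidence needs the same event question put to everyone in the denominator. In the plan as written, whether a participant is asked depends on how unwell they feel overall or on their own initiative. The SAP safety population (Table 3) is participants who consented and were infused. The denominator therefore includes people who were never asked, while the numerator is drawn mainly from those who scored very low, reported worsening or called in.

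Safety of at-home infusion is the first purpose named in Protocol section 2. A low figure that looks complete could be taken as reassurance. An event that leaves the overall score at 4 or above is the kind most easily missed.

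**Working it through.** No figure in the documents bears on this point: there is no expected event rate, response rate or precision target to reproduce. The check is a comparison of texts.

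**Step 1. Who is asked about events after the nurse leaves?**

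| Route | Where | Who is reached |
|---|---|---|
| Daily 1-10 score | Protocol 6.1, Appendix 3 | Everyone, but it is a global score and not an event question |
| Symptom list at outreach | Protocol Appendices 3 and 4 | Scores of 1-3, with deferral possible |
| Phone follow-up | Protocol 9.1 | Those who mark feeling worse |
| Contact numbers | Protocol 6.1, 7.1, 9.1 | Those who choose to call |
| Post Infusion CRF | SAP Appendix 2 | Those who have a symptom, reaction or event |
| United in Research tracking | Protocol Appendix 1 | Not stated: no form, schedule or data source |
| Day 28 notification | Protocol 6.1 | Everyone, but it offers an optional survey on study experience |

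No row is a scheduled event question to all infused participants. Protocol Table 1 does list patient-reported data running to Day 28, but it names no instrument or question. Protocol 4.4 (Phase II.B) would derive event type partly from the 1-10 score, and a single global score cannot tell nausea from itching.

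**Step 2. Does the form match the SAP's event list?**

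| SAP 5.10.1.2 event | Own item on the Protocol Appendix 4 form |
|---|---|
| Nausea | Yes (appears twice) |
| Diarrhea | Yes |
| Headache | Yes |
| Vomiting | None so labelled |
| Dizziness | No |
| Pruritus | No |

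Three of six have no labelled item. If the second nausea entry is a mislabelled vomiting item or an artefact of text extraction, at least dizziness and pruritus (two of six) still have none. They can be recorded only through the closing open question. The SAP copy of the form differs: it adds loss of sensation and loss of strength and, as extracted, shows only headache of the six. Some of that may be extraction loss, so no weight is put on that count.

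**Step 3. Do the SAP sources reach the records?** Set against Protocol 6.5.5, SAP 5.10 omits the patient self-reported source. ProtectWell stays in SAP Table 1 but is not an adverse-event source in 4.7 or 5.10. The clinical team's follow-up records are not listed as a source. SAP 5.14 does not mention the difference.

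**Step 4. Direction of the bias.** Let f be the share of participants with at least one event who are contacted at follow-up (all assumed captured), and s the share of the rest who are captured by other routes. Then

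reported incidence / true incidence = f + (1 − f)s.

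This is below 1 unless f or s equals 1. The documents give neither value. For illustration only:

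- f = 0.10, s = 0.10: 0.10 + 0.90 × 0.10 = 0.19
- f = 0.50, s = 0.50: 0.50 + 0.50 × 0.50 = 0.75

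Under those assumed values a true 10% would be reported as 1.9% to 7.5%. The range reflects the assumptions and is not an estimate for this study. Full capture at follow-up is itself generous, because Appendix 3 allows outreach to be deferred.

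**The case against.** The strongest reply is that several routes exist and the objective is only to describe. Protocol 9.1 prompts a call whenever a participant marks feeling worse, and the caller must then consider whether a side effect is involved. Participants can phone in, there is a dedicated Post Infusion CRF, and the open question on the form can record any event. Infusion reactions are a separate objective with nurse-collected data. All of this stands, and it rules out some stronger readings:

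- A reader might infer that participants are asked only after a low score. Section 9.1 does not support that. But someone who feels the same or better, with a score of 4-10, is asked under neither text.
- A reader might infer that the objective cannot be met. SAP 5.10 promises descriptive statistics on whatever data are obtained, and some events will be captured. Incomplete ascertainment limits what the result means; it does not make the objective unattainable.
- A reader might infer that the SAP discards patient reports. This is not shown. For hospitalization, the SAP's primary analysis section (5.8.1.3) names pharmacy data where Protocol 6.5.2 had patient-reported data. The Post Infusion CRF also sits beside the pharmacy and nursing forms, so participant reports may be in that data set. The SAP does not say so.
- The CRFs are attachments that are not reproduced in the text, so how they elicit events is unknown. The SAP describes the Post Infusion form as conditional on the participant having a symptom, reaction or event.

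What remains is that none of the described routes puts an event question to everyone.

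**Conclusion.** The point holds as a matter of selective under-ascertainment. The reported Day 28 figure will be too low, chiefly because of participants who score 4-10 and neither report feeling worse nor call in. It should not be presented as an incidence among all infused participants. The form's gaps and the SAP's source list add to the problem. The undeclared difference in sources between Protocol 6.5.5 and SAP 5.10 stands independently of the rest.

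The size cannot be estimated from the documents; only the downward direction can be stated. The conclusion assumes that the attachments and the undefined United in Research tracking contain no scheduled event question for all participants. If one does, the protocol and SAP should say so, and most of the concern falls away. For a descriptive objective this is a change that should be made; it is not a fatal defect.

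**What to change.** 1. Add one yes/no item on new symptoms or side effects, with a tick list, to the existing daily ProtectWell check for all infused participants. Repeat it at the Day 28 contact.
2. Align the symptom form with the six events in SAP 5.10.1.2, and use the same form in both documents.
3. In SAP Table 1, 4.7 and 5.10, name ProtectWell and the UHG R&D clinical follow-up records as adverse-event sources. State whether participant reports are held in the pharmacy data, and record the source change in 5.14.
4. If item 1 is not done, label the result as events reported spontaneously or at triggered follow-up, and do not call it incidence.

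The follow-up triggers in Protocol 9.1 and Appendix 3 differ and the sponsor must reconcile them. No trigger is proposed here, and item 1 does not require one to change.

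The cost is one app question, a few form items and some SAP source lines. The downside is slightly more participant burden and more minor events to process. Items 3 and 4 are document edits only.
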